Safety Analyses: The Safety Population will be used in the analysis of safety data. Data will be listed by subject and treatment and summarized by treatment. No formal statistical comparisons will be made for safety data. The number and proportion of subjects with TEAEs will be summarized by treatment, system organ class, and preferred term for all TEAEs, all TEAEs considered by the Investigator to be related to study drug, all SAEs, and all TEAEs leading to study drug discontinuation. All TEAE summaries will include information for AEs that occurred after administration of the first dose of study drug until completion of the final study visit. Data listings will be provided for subjects who discontinued the study due to an AE and for subjects with an SAE. Selected laboratory data will be analyzed using descriptive summary statistics and will be presented by study visit and treatment group, including the number of non-missing observations, mean and standard deviation, median, upper and lower quartiles, minimum and maximum for values and changes from Baseline. Categorical safety data will be analyzed using frequency tables and, if applicable, shift tables.

**Functional Outcomes and Quality of Life Analysis:** Change from Baseline in the subject reported DLQI, PSD, SF-36, and Peak Pruritus-NRS scores will be analyzed using an ANCOVA model with treatment as a main effect, and baseline as a covariate

Pharmacokinetic Analyses: Plasma concentration data will be listed and summarized by study visit.

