### 4.6.1. Reasons for Withdrawal from the Study

Study drug will be discontinued for any of the following reasons:

- Subject has an AE that is considered to be related to study drug or procedures AND is severe enough to warrant treatment discontinuation, as determined by the Investigator (Section 8.1).
- Subject requires concurrent prohibited medication during the study. If, in the opinion of the Investigator and the study Medical Monitor, such medication will not interfere with the conduct or interpretation of the study or compromise the safety of the subject, then the subject may continue to receive study drug. If the subject is discontinued from study drug, they may remain in the study for safety assessments as needed, at the discretion of the Investigator and Medical Monitor.
- Pregnancy
- Any Grade 3 or 4 AE considered causally related to study drug (Section 8.2.2)

Study drug may be discontinued for any of the following reasons:

• Subject noncompliance

- Investigator noncompliance
- Discontinuation of the study at the request of the Sponsor, regulatory agency, or an Institutional Review Board (IRB)/Independent Ethics Committee (IEC).

If a subject meets a withdrawal criterion during treatment, an Early Termination visit will be required (Section 7.5).

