#### 8.1.3. Adverse Events of Special Interest

In prior clinical studies, the following AEs have been identified as AEs of particular clinical importance and will be reported as AESIs in this study; in each case study drug may be discontinued, based on Investigator judgment, and may be restarted when the event resolves:

- Contact dermatitis: the study site should collect location, duration, size, associated symptoms (itching, burning, pain), severity (mild, moderate, severe), and photograph the affected site (if possible). If the subject contacts the study site to report significant skin irritation at or near the site of study drug application between study visits, the subject should be brought in for an unscheduled visit, if possible.
- Folliculitis: the study site should collect the location, duration, size, associated symptoms (itching, burning, pain), severity (mild, moderate, severe), indicate whether pustular, and photograph the affected site (if possible).
- Headache: the study site should collect duration, severity (mild, moderate, severe), onset, and location (e.g., frontal, temporal, occipital, diffuse).

Additional AESIs may be identified by the Drug Safety Physician and if applicable by the Clinical Study Team Physician during the evaluation of safety data for the Clinical Study Report. For each AESI, a narrative may be written and included in the Clinical Study Report.

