#### 10.4.3. Safety Analyses

The Safety Population will be used in the analysis of safety data. Data will be listed by subject and treatment and summarized by treatment. No formal statistical comparisons will be made for safety data.

The number and proportion of subjects with TEAEs will be summarized by treatment, system organ class, and preferred term for all TEAEs, all TEAEs considered by the Investigator to be related to study drug, all SAEs, and all TEAEs leading to study drug discontinuation. Summaries of AEs will be presented separately for double-blind and open-label treatment phases. All AE summaries will include information for AEs that occurred after administration of the first dose of study drug until completion of the final study visit. Data listings will be provided for subjects who discontinued the study due to an AE and for subjects with an SAE.

Selected laboratory data will be analyzed using descriptive summary statistics and will be presented by study visit and treatment group, including the number of non-missing observations, mean and SD, median, upper and lower quartiles, minimum and maximum for values and changes from Baseline. Categorical safety data will be analyzed using frequency tables and, if applicable, shift tables.

Vital signs will be listed by subject and summarized by visit.

Mean scores from the LTS will be summarized by visit.

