#### 12.9.1 Adverse Events

AE terms will be coded using the MedDRA dictionary. A treatment-emergent AE (TEAE) is defined as an AE that starts after the first dose of study medication. For subjects not rolling over to Open-label study, all reported AEs will be included in the Double-Blind phase summaries. For subjects rolling over to the Open-label study, all AEs with an onset date on or before the Week 12 visit date will be included in the Double-Blind phase summaries.

If relationship to treatment is missing, the event will be conservatively treated as related to study drug. Missing severity will be imputed to the highest severity level (most severe).

All AEs will be listed by treatment and by subject, detailing the verbatim term given by the investigator, the preferred term (PT), system organ class (SOC), onset date and time, end date and time, duration (days), CTCAE grade, outcome, relationship to study drug/treatment, action taken with study drug/treatment, other action taken to treat the event, seriousness and criteria for seriousness. Serious AEs (SAEs), TEAEs leading to study discontinuation, TEAEs related to study drug will also be listed separately. The following adverse event of special interest (AESIs) will be identified and listed separately: contact dermatitis, folliculitis, and headache.

AEs will be summarized by treatment and overall as incidence rates of:

- Any AE
- Any TEAE
- Any AESIs
- Any treatment-related TEAE, including definitely, probably, and possibly related
- Any TEAE leading to study drug discontinuation
- Any SAE (non-Fatal)
- Any serious TEAE
- Death
- Treatment-related Serious TEAE
- Serious TEAE leading to study drug discontinuation

Individual PTs will be summarized by treatment according to the following:

- All TEAEs by SOC in alphabetical order and PT in descending order of combined frequency (also for treatment-related TEAEs, TEAEs leading to study discontinuation and serious TEAEs)
- All TEAEs by SOC, PT, and maximum CTCAE grade
- All TEAEs by SOC, PT, and maximum causality (not related, related) to the study drug

In addition, TEAEs and serious TEAEs will be summarized by SOC (alphabetical order) and PT (descending order) for the following subgroups:

- Age (<65 and >=65 years old)
- Sex
- Race (White, Other)

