### 13. CHANGES FROM THE PROTOCOL AND PLANNED ANALYSES

The protocol specified change over time in physical component score and mental component score as measured by the SF-36 questionnaire as an exploratory endpoint. Scoring rules for the RAND 36-Item Health Survey (Version 1.0) are provided for the eight domain scores but not for the physical component score or the mental component score. Hence, summaries of the eight domain scores are planned.

No other changes from the protocol in planned analyses are noted. Any additional statistical analyses to handle modifications to study conduct and/or missing data due to the COVID-19 pandemic have been documented in Section 12.11 above in this SAP and will be finalized prior to database lock and unblinding of the study.

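### SAP 12.9.1 builds the SOC/PT discontinuation table on TEAEs that led to leaving the study, whereas protocol 10.4.3 requires it for TEAEs that led to stopping study drug

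*SAP*

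**What the plan says.** Protocol 10.4.3 (Safety Analyses) states that the number and proportion of subjects with TEAEs will be "summarized by treatment, system organ class, and preferred term for all TEAEs", and names three further categories for the same treatment: "all TEAEs considered by the Investigator to be related to study drug, all SAEs, and all TEAEs leading to study drug discontinuation". The Statistical Methods part of the synopsis repeats the last of these: "all TEAEs leading to study drug discontinuation". For listings, protocol 10.4.3 asks for something different: subjects who left the study because of an AE, and subjects with an SAE.

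SAP 12.9.1 (Adverse Events) has three relevant outputs.

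- The overall AE summary has one row for any TEAE that led to stopping study drug and one for serious TEAEs that did so. Neither carries terms.
- The SOC/PT summary is planned for all TEAEs and "also for treatment-related TEAEs, TEAEs leading to study discontinuation and serious TEAEs".
- Separate listings include TEAEs that led to leaving the study.

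SAP 13 reports the SF-36 scoring change, refers to the COVID-19 additions, and otherwise says "No other changes from the protocol in planned analyses are noted".

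**The concern.** The protocol's term-level discontinuation table is defined by stopping drug. The SAP's is defined by leaving the study. If these were two names for one event, the difference would be only wording. They are not: protocol 4.6 allows a subject to stop treatment, to leave the study, or both, and SAP 12.1 counts withdrawal from treatment and withdrawal from the study separately, each with its reasons.

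What is at stake is one safety table that the protocol requires. The events that make patients stop a topical drug are a central tolerability result, and protocol 1.1.2 says the study is intended to support registration. Under the SAP as written, the report would give the number of subjects who stopped drug for a TEAE, but the SOC/PT table next to it would describe a different set of events.

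**Working it through.** No sample size, power or event count enters this point, so the check is a comparison of texts.

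**Step 1. Set the outputs side by side.** Let D be the TEAEs that led to stopping study drug and S the TEAEs recorded as the cause of leaving the study.

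| Output | Protocol 10.4.3 | SAP 12.9.1 |
|---|---|---|
| SOC/PT discontinuation table | D | S |
| Overall incidence rows | not specified | D |
| Separate discontinuation listing | subjects who left the study for an AE | S |
| All-AE listing with action taken on study drug | data listed by subject; fields not specified | all AEs, so both D and S |

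The only conflict is in the first line. The listing in the third line agrees with the protocol.

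**Step 2. Are D and S the same set?** Four places bear on this.

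- Protocol 4.6 and 4.6.2 speak of stopping drug and/or leaving the study, so either can happen without the other.
- SAP 12.1 tabulates the two withdrawals separately.
- Protocol 8.1.3 says of the three AESIs that "study drug may be discontinued, based on Investigator judgment, and may be restarted when the event resolves". A restart presupposes that the subject is still in the study.
- Protocol 4.6.1 says of subjects taken off drug that "they may remain in the study for safety assessments as needed". This sentence belongs to the bullet on prohibited medication, so it shows that the two states can separate but does not speak to AE-driven stops.

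The documents therefore do not treat D and S as identical.

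**Step 3. What follows for reconciliation.** The SAP's overall row counts subjects with an event in D, and its SOC/PT table counts subjects with an event in S. The two are sure to describe the same subjects only if D = S. Any event in D but not in S is absent from the SOC/PT discontinuation table.

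**Step 4. Size.** The number of events in D but not in S lies between 0 (every TEAE that stops drug is also recorded as the cause of study withdrawal) and all of D (none is). The documents give no expected rate of AE-driven drug discontinuation and no fraction of such subjects who stay in the study, so the range cannot be narrowed.

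**Step 5. Where the omitted events still appear.** Under SAP 12.9.1 they remain in the SOC/PT table of all TEAEs, in the tables by grade and by causality, and in the all-AE listing, which shows the term and the action taken with study drug. For contact dermatitis, folliculitis and headache, the AESI summaries also tabulate action taken, with each type reported separately. What is missing is an SOC/PT breakdown of drug-stopping events across all terms.

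**The case against.** The best case against the point is that D and S may be nearly the same in practice. Protocol 4.6.1 lists reasons for stopping drug under a heading about withdrawal from the study, and requires an Early Termination visit when a withdrawal criterion is met. Section 4.6.2 ties premature drug discontinuation to that visit. Section 7.5 and the footnote to the Schedule of Assessments describe it as the visit for subjects who leave the study. For Grade 3 and Grade 4 events that end treatment permanently, section 8.2.1.2 encourages withdrawal evaluations. A stop with restart under 8.1.3 may be recorded as an interruption and so not fall in D at all. Safety analysis is descriptive, with no formal comparison, and SAP 12.9.1 uses the drug-discontinuation wording twice in its own incidence list, so the SOC/PT wording may be a slip.

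Most of this stands as a limit on size: the gap may be small. It does not remove the mismatch, because the SAP governs programming and names two different categories within one section. If it is a slip, that is a reason to correct it.

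Three stronger readings are tempting and are not supported.

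- A reader might infer that the SAP's study-discontinuation listing is a second deviation. It is not; protocol 10.4.3 asks for a listing of subjects who left the study for an AE.
- A reader might infer that the report would not show which AEs stopped treatment. The all-AE listing shows it event by event, and the AESI summaries tabulate it for the three AESIs.
- A reader might infer that the omitted events fall mainly in the tapinarof arm. Protocol 1.1.1 reports only that TEAEs overall were more frequent with tapinarof than with vehicle in the Phase 2b studies; it gives no drug-discontinuation rates by arm.

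**Conclusion.** The SAP is wrong as written on one table. It replaces a protocol-required SOC/PT summary of TEAEs that led to stopping study drug with one of TEAEs that led to leaving the study, and SAP 13 does not declare the change. As a result, the SOC/PT table need not reconcile with the overall drug-discontinuation row in the same section. Confidence is high for the mismatch, which rests on the text alone. The consequence depends on how often a TEAE stops drug without being recorded as the cause of study withdrawal, and the documents do not say. No endpoint, test, analysis population or data collection is affected.

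**What to change.** In SAP 12.9.1, define the SOC/PT discontinuation table by TEAEs that led to stopping study drug, taken from the action-taken field that the all-AE listing already carries. State which recorded actions count, so that the overall row and the SOC/PT table use the same flag and temporary stops are handled alike in both. Keep the study-discontinuation listing, which protocol 10.4.3 calls for; a matching drug-discontinuation listing is optional. If the study-discontinuation table is what is intended, declare and justify that departure in SAP 13.

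The cost is one phrase in the SAP and one table filter. No new data are needed.

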### Safety:

- Incidence, frequency, and duration of treatment emergent adverse events (TEAEs) and serious adverse events (SAEs)
- Clinically significant change from Baseline in laboratory values
- Clinically significant change from Baseline in vital signs
- Mean LTS scores by visit

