### 9. HANDLING OF MISSING DATA

### Imputation of Start and End Dates of Adverse Event (AE)

To calculate duration of Adverse Events, the following rules will be used where applicable to impute partial or completely missing start dates or end dates:

- If only the day is missing for a start date, the 1st of the month will be imputed. If the new estimated date falls before the date of first dose, while the known month and year match the month and year of the first dose, the date of first dose will be used as the new estimated date. The AE will be considered as a treatment-emergent AE (TEAE).
- If only the day is missing for an end date, the last day of the month will be imputed. If the new estimated date falls after the date of last study visit, the date of last study visit will be used as the new estimated date. Last study visit is defined as the Week 12 visit for those who elect to participate in the open-label long-term study, or the Week 16 Follow-up visit for those who fail to qualify for participation in the open-label study, or who qualify to participate but ultimately elect not to enroll.
- If both the day and the month are missing for a start date or end date, no imputation will be used, and the duration will not be calculated. However, if the year of start is the same or greater than the year of the first dose date, the AE will be considered as treatment emergent.

• If the start date or end date is completely missing, duration will not be calculated. However, an event with completely missing start date will be considered as treatment emergent.

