At each level of summarization, a subject will be counted once if he/she reported one or more events. The severity of TEAEs and relationship to study drug will be summarized in a similar manner. For summaries of relationship to study drug, a subject will be classified according to the closest relationship. For summaries of TEAE CTCAE grade, a subject will be classified according to the worst grade.

For AESIs, summarization will be more extensive, reflecting the more detailed information collected. Information summarized will include number of events per subject, earliest onset day, duration (in days), causality, grade and seriousness of AESIs, outcome, actions taken with study drug, assorted physical characteristics of the AESIs, and demographic/baseline characteristics and PGA status of the subjects experiencing them. Each type of AESI will be summarized separately. If a subject has more than one treatment-emergent occurrence of an AESI, the subject's maximum duration, highest levels of causality and seriousness, maximum grade and generally the most extreme level of each characteristic will be summarized. If an AESI was ongoing at EOS, it will not be included in the duration summary.

A Kaplan-Meier figure will be generated for each AESI of time to first event. Subjects not experiencing the AESI will be censored at the date of study completion or discontinuation.

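### Leaving AESIs that are ongoing at end of study out of the duration summary biases reported durations short for any AESI type with unresolved events; the effect is small for events of a few days and can be large for events of weeks

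*SAP*

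**What the plan says.** SAP 12.9.1 names the AESIs: they "will be identified and listed separately: contact dermatitis, folliculitis, and headache". It plans a fuller summary for them than for other adverse events: "Information summarized will include number of events per subject, earliest onset day, duration (in days), causality, grade and seriousness of AESIs, outcome", with each AESI type handled separately. Two rules then shape the duration figure.

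- Repeat events: "If a subject has more than one treatment-emergent occurrence of an AESI, the subject's maximum duration, highest levels of causality and seriousness" and similar extremes are what is summarised.
- Unresolved events: "If an AESI was ongoing at EOS, it will not be included in the duration summary".

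No other rule offsets the second one. SAP Section 9 imputes an end date only when the day alone is missing; otherwise, "If the start date or end date is completely missing, duration will not be calculated". The one time-to-event display for AESIs concerns onset, not duration: "A Kaplan-Meier figure will be generated for each AESI of time to first event".

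Section 9 also fixes a subject's last study visit, for end-date imputation: it "is defined as the Week 12 visit for those who elect to participate in the open-label long-term study, or the Week 16 Follow-up visit" when the subject does not enter the open-label study. Subjects who terminate early are not named there. EOS is expanded in the SAP's abbreviation list but not defined per subject.

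Duration is part of the protocol's first safety endpoint ("Incidence, frequency, and duration of treatment emergent adverse events (TEAEs) and serious adverse events (SAEs"), and Protocol 8.1.3 has sites collect it for each AESI.

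**The concern.** An event enters the duration summary only if it ends before the subject's follow-up does. For a given onset date, a long event is less likely to meet that condition than a short one, so the retained events under-represent long durations. The cut-off also differs between subjects. Those who roll over stop at Week 12, and their events count if onset is on or before the Week 12 visit (SAP 12.9.1), so events starting late in treatment are very likely to be dropped. Subjects who do not roll over have about four more weeks in which an event can resolve. The reported duration thus depends partly on who rolled over.

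At stake is a descriptive but clinically relevant statement: how long contact dermatitis, folliculitis or headache lasts in each arm. If one arm has more persistent events, more of its events are left out and the difference in duration looks smaller than it is. The rule also runs against the rest of SAP 12.9.1, which takes the worst case for missing severity, missing causality and repeat events.

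**Working it through.** The plan states no AESI duration or ongoing rate, so there is no figure to reproduce. The check covers direction, then size.

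**Direction.** Let T be an event's true duration and U the time from onset to the subject's last visit. The rule keeps events with T ≤ U, so a duration t is kept with probability P(U ≥ t), which cannot increase with t. If T and U are independent, the kept durations are stochastically shorter than, or equal to, the true ones. This needs no particular distribution.

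**Size.** Inputs from the documents: Week 12 target Day 85 and Week 16 target Day 113 (SAP 11.4). Assumptions not in the documents: onset uniform over Days 1 to 85, exponential T with mean m, one event per subject. U is then uniform on [a, b], with a = 0 and b = 84 for the Week 12 cut-off, and a = 28 and b = 112 for Week 16.

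- Share ongoing: p = (m/84)(e^(−a/m) − e^(−b/m))
- Mean of kept events: {m − (m/84)[(a+2m)e^(−a/m) − (b+2m)e^(−b/m)]} / (1 − p)

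For m = 28:

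- Week 12: p = (28/84)(1 − 0.0498) = 0.317. Mean = {28 − (28/84)[56 − 140 × 0.0498]} / 0.683 = 11.66 / 0.683 = 17.1.
- Week 16: p = (28/84)(0.3679 − 0.0183) = 0.117. Mean = {28 − (28/84)[84 × 0.3679 − 168 × 0.0183]} / 0.883 = 18.73 / 0.883 = 21.2.

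The same formulas for other true means:

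| True mean (days) | Week 12: ongoing | Week 12: mean shown | Week 16: ongoing | Week 16: mean shown |
|---|---|---|---|---|
| 3 | 3.6% | 2.9 | 0.0% | 3.0 |
| 14 | 16.6% | 11.2 | 2.2% | 13.0 |
| 28 | 31.7% | 17.1 | 11.7% | 21.2 |
| 42 | 43.2% | 20.0 | 22.2% | 25.8 |

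For m = 28 the true median is 28 × ln 2 = 19.4 days. The rule shows 12.8 (Week 12) or 16.3 (Week 16).

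**Other distributions.** Simulation with 400,000 events per scenario, exponential and lognormal (sigma 1), gives these medians under the SAP rule:

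| True median (days) | Cut at Day 85 | Cut at Day 113 |
|---|---|---|
| 1 | 1.0 | 1.0 |
| 7 | 6.1–6.2 | 6.8–6.9 |
| 14 | 10.5–11.0 | 12.7–12.9 |
| 28 | 15.4–17.8 | 20.2–21.4 |
| 56 | 19.3–25.8 | 26.7–31.3 |

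Event-level Kaplan-Meier with censoring at the cut-off returned the true median to within 0.5 day in every scenario.

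**Between arms.** Suppose true means of 14 and 42 days, a gap of 28. From the first table the gap shown is 20.0 − 11.2 = 8.8 days (Week 12) or 25.8 − 13.0 = 12.8 days (Week 16).

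**Per-subject maximum.** Assume two independent events per subject, m = 28, Week 12 cut-off. The true median of the longer event is 34.4 days. The maximum over resolved events shows about 17.7. Kaplan-Meier applied to each subject's longest observed duration gives about 31.2: much closer, but still short. For m = 42 the three figures are about 51.7, 20.0 and 45.0. Censoring therefore has to be applied to events, not to per-subject maxima.

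**The case against.** The strongest reply is that unresolved events are not concealed. SAP 12.9.1 summarises AESI outcome by type, and the outcome categories in Protocol 8.3.2 separate unresolved and resolving events from resolved ones. Onset, end, duration and outcome are listed for every adverse event. SAP 12.9 rules out formal safety comparisons. All of this stands and limits the consequence. It does not correct the duration statistic, which the SAP does not require to be labelled as covering resolved events only.

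Several stronger readings are tempting, and the documents do not support them.

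- *Durations of all three AESIs are biased short.* With nothing ongoing at the cut-off there is no bias, and for brief headaches it is negligible.
- *The rule removes the longest events.* Removal depends on duration relative to time left. A one-day headache starting the day before the last visit can be dropped, while a 70-day dermatitis starting in Week 1 is kept.
- *A between-arm difference is hidden.* In the example above it is attenuated, and an excess of unresolved events would show in the outcome summary.

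The cut-off itself is partly inferred. Section 9 gives the Week 12 and Week 16 definition for date imputation, the protocol's end of study (3.2, 7.6) refers to the last active subject, and adverse events are followed to resolution or stabilisation (8.3.2). If later resolution dates were used, fewer events would be dropped. That ambiguity is a further reason to define the cut-off.

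**Conclusion.** The concern holds in a limited form. The rule shortens reported AESI durations whenever events are ongoing at the cut-off, and nothing else in the SAP corrects that statistic. The direction rests only on duration being independent of remaining follow-up. The size rests on assumed onset and duration distributions: next to nothing for events of a few days, and for a true mean of 28 days a shown mean about 39% too short at Week 12 (17.1/28 = 0.61) or 24% too short at Week 16 (21.2/28 = 0.76).

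The figures are for single events, whereas the SAP summarises a per-subject maximum. It does not say whether a subject with one resolved and one ongoing occurrence is summarised by the resolved one or left out. Incidence, efficacy and all formal tests are untouched. This is a cheap improvement to descriptive safety reporting, not a threat to the trial's conclusions.

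**What to change.** Replace the sentence in SAP 12.9.1 with wording to this effect:

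> AESI duration will be summarised at the event level by Kaplan-Meier (median and quartiles) for each AESI type and arm. Events ongoing at the subject's last study visit (Week 12 for rollover subjects, Week 16 follow-up for others, last visit attended for early-terminated subjects) will be censored at that visit. The number and percent ongoing will be shown alongside.

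If a per-subject maximum duration is kept, label it 'resolved events only'.

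The cost is one SAP sentence and one extra procedure call. No new data are needed, and Kaplan-Meier is already planned for AESI onset. There are two downsides. Subjects with several events contribute more than once, so the summary should stay descriptive. Kaplan-Meier also assumes that censoring is unrelated to duration, which is doubtful for a subject who leaves because of the event; showing the number ongoing lets the reader judge this.
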